## **10.2 ANALYSIS OF SECONDARY EFFICACY ENDPOINTS**

### **10.2.1 Investigator-Assessed ORR by RECIST v1.1**

The best overall response and the point estimators of investigator-assessed ORR by RECIST v1.1 with corresponding 95%, two-sided CIs, will be provided. The proportion difference for the ORR by RECIST v1.1 with corresponding 95%, two-sided CIs will be provided.

The following table and figures will be provided:

- Investigator-Assessed Response by RECIST v1.1
- Swimmer's Plot of Investigator-Assessed Response by RECIST v1.1 for ORR Responders
- Waterfall Plot of Maximum Percent Reduction from Baseline in Individual Sum of the Longest Diameters of Target Lesions, Assessed by Investigator
- Spider Plot of Individual Percent Change from Baseline in Sum of the Longest Diameters of Target Lesions, Assessed by Investigator

The following efficacy listings will be provided:

- Investigator-Assessed Target Lesions
- Investigator-Assessed Non-Target Lesions

Idera Pharmaceuticals, Inc.  
Statistical Analysis Plan  
Protocol Number: 2125-MEL-301

---

- Investigator-Assessed New Lesions
- Investigator-Assessed Response by RECIST v1.1
- Investigator-Assessed Response by irRECIST
- Investigator-Assessed RECIST v1.1 Tumor Response Endpoints

### **10.2.2 Comparison of Best Overall Responses between Independent Review and Investigator**

A summary of the differences in the best overall responses by RECIST v.1.1 between independent review and the investigator assessment will be presented by treatment arm and overall in a table format with the number and percentage of independent reviewer responses presented side-by-side with those for the investigator responses. Comparison of the ORR responders and non-responders will be performed by treatment arm and overall to evaluate the number and percentage of concordant and discordant pairs of ORR responses (CR/PR versus non-CR/PR) between the independent reviewer and investigator.

The following summary tables will be provided:

- Concordance of Best Overall Response by Independent Reviewer and Investigator
- Concordance of ORR by Independent Reviewer and Investigator

### **10.2.3 Analysis of Injected and Non-injected Lesions**

For each subject, the sum of longest diameters (SLD) will be calculated separately among the injected lesions and the non-injected lesions at each nominal visit only in the combination treatment arm (ipilimumab with IMO-2125). Note that the sum of the shortest distance (SSD) will be calculated for lymph nodes instead and will be summarized together with SLD in the analysis. For each subject, the percent reduction from baseline in the SLD/SSD, and the paired difference in the percent reduction between the injected and non-injected lesions will be calculated and summarized by study visit. Any new lesions noted post-baseline will be excluded from the calculation. Any non-target lesions without measurement at baseline will be excluded from this analysis. The maximum percent reduction in SLD/SSD by injection status will be presented graphically in a waterfall plot for the ORR responders assessed by independent-reviewer using RECIST v.1.1 (i.e., those with best overall response of CR or PR).

The following table and figure will be provided:

- Paired Difference of Percent Reduction from Baseline in Individual Sum of the Longest Diameters Between Injected and Non-injected Lesions

Idera Pharmaceuticals, Inc.  
Statistical Analysis Plan  
Protocol Number: 2125-MEL-301

---

- Waterfall Plot of Maximum Percent Reduction from Baseline in Individual Sum of the Longest Diameters of Measurable Lesions by Injection Status, ORR Responders Assessed by Independent Reviewer (injection status presented side-by-side)
- Spider Plot of Individual Percent Change from Baseline in Sum of the Longest Diameters of Measurable Lesions by Injection Status, Assessed by Investigator (separate page by injection status)

The following efficacy listing will be provided:

- Sum of the Longest Diameters and Percent Change from Baseline in SLD by Injection Status

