All sites of disease must be assessed at baseline. Baseline assessments should be done as close as possible prior to study start. For an adequate baseline assessment, all required scans must be done within 28 days prior to treatment and all disease must be documented appropriately. If baseline assessment is inadequate, subsequent statuses generally should be indeterminate.

5. Target Lesions

All measurable lesions up to a maximum of 2 lesions per organ, 5 lesions in total, representative of all involved organs, should be identified as target lesions at baseline. Target lesions should be selected on the basis of size (longest lesions) and suitability for accurate repeated measurements. Record the longest diameter for each lesion, except in the case of pathological lymph nodes for which the short axis should be recorded. The sum of the diameters (longest for non-nodal lesions, short axis for nodal lesions) for all target lesions at baseline will be the basis for comparison to assessments performed on study.

- If two target lesions coalesce the measurement of the coalesced mass is used. If a large target lesion splits, the sum of the parts is used.
- Measurements for target lesions that become small should continue to be recorded. If a target lesion becomes too small to measure, 0 mm should be recorded if the lesion is considered to have disappeared; otherwise a default value of 5 mm should be recorded.

NOTE: When nodal lesions decrease to <10 mm (normal), the actual measurement should still be recorded.

6. Non-target Disease

All non-measurable disease is non-target. All measurable lesions not identified as target lesions are also included as non-target disease. Measurements are not required but rather assessments will be expressed as ABSENT, INDETERMINATE, PRESENT/NOT INCREASED, INCREASED. Multiple non-target lesions in one organ may be recorded as a single item on the case report form (eg, 'multiple enlarged pelvic lymph nodes' or 'multiple liver metastases').

B. Objective Response Status at Each Evaluation

Disease sites must be assessed using the same technique as baseline, including consistent administration of contrast and timing of scanning. If a change needs to be made the case must be discussed with the radiologist to determine if substitution is possible. If not, subsequent objective statuses are indeterminate.

1. Target Disease

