- Complete Response (CR): Complete disappearance of all target lesions with the exception of nodal disease. All target nodes must decrease to normal size (short axis <10 mm). All target lesions must be assessed.
- Partial Response (PR): Greater than or equal to 30% decrease under baseline of the sum of diameters of all target measurable lesions. The short diameter is used in the sum for target nodes, while the longest diameter is used in the sum for all other target lesions. All target lesions must be assessed.
- Stable: Does not qualify for CR, PR or Progression. All target lesions must be assessed. Stable can follow PR only in the rare case that the sum increases by less than 20% from the nadir, but enough that a previously documented 30% decrease no longer holds.
- Objective Progression (PD): 20% increase in the sum of diameters of target measurable lesions above the smallest sum observed (over baseline if no decrease in the sum is observed during therapy), with a minimum absolute increase of 5 mm.
- Indeterminate. Progression has not been documented, and
 - one or more target measurable lesions have not been assessed;
 - or assessment methods used were inconsistent with those used at baseline;
 - or one or more target lesions cannot be measured accurately (eg, poorly visible unless due to being too small to measure);
 - or one or more target lesions were excised or irradiated and have not reappeared or increased.

2. Non-target Disease

- CR: Disappearance of all non-target lesions and normalization of tumor marker levels. All lymph nodes must be 'normal' in size (<10 mm short axis).
- Non-CR/Non-PD: Persistence of any non-target lesions and/or tumor marker level above the normal limits.

- PD: Unequivocal progression of pre-existing lesions. Generally the overall tumor burden must increase sufficiently to merit discontinuation of therapy. In the presence of SD or PR in target disease, progression due to unequivocal increase in non-target disease should be rare.
- Indeterminate: Progression has not been determined and one or more non-target sites were not assessed or assessment methods were inconsistent with those used at baseline.

3. New Lesions

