#### **8.2.8.2 Injected and Non-injected Lesions**

To explore the treatment effect of IMO-2125 between the measurable injected and non-injected lesions, the sum of the longest diameters will be calculated separately among the injected lesions and the non-injected lesions for each subject at each nominal visit in the combination treatment arm (ipilimumab with IMO-2125). Due to the potentially different numbers of injected and non-injected lesions involved in the calculation for each subject, the percent reduction from baseline in the sum of the longest diameters will be used for the analysis. For each subject, the paired difference in the percent reduction between the injected and non-injected lesions will be calculated. Any measurable new lesions noted post-baseline will be excluded from the calculation.

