14.1.2.4 Swimmer's Plot of Investigator-Assessed Response by RECIST v1.1 for ORR Responders, Intent to Treat Analysis Set	ORR, Final
14.1.2.5 Waterfall Plot of Maximum Percent Reduction from Baseline in Individual Sum of the Longest Diameters Assessed by Investigator, Intent to Treat Analysis Set	ORR, Final
14.1.2.6 Spider Plot of Individual Percent Change from Baseline in Sum of the Longest Diameters, Assessed by Investigator, Intent to Treat Analysis Set	ORR, Final
14.1.3 Waterfall Plot of Maximum Percent Reduction from Baseline in Individual Sum of the Longest Diameters Among Measurable Lesions by Injection Status for ORR Responders, Intent to Treat Analysis Set	ORR, Final
14.1.4.1 Kaplan-Meier Plot of Independent Reviewer-Assessed DoR by RECIST v1.1 for ORR Responders, Intent to Treat Analysis Set	ORR, Final
14.1.4.2 Kaplan-Meier Plot of Investigator-Assessed DoR by RECIST v1.1 for ORR Responders, Intent to Treat Analysis Set	ORR, Final
14.1.5 Kaplan-Meier Plot of Overall Survival, Intent to Treat Analysis Set	IDMC, Final
14.1.6 Forest Plot of Hazard Ratios for Overall Survival by Subgroup, Intent to Treat Analysis Set	Final

Idera Pharmaceuticals, Inc.  
 Statistical Analysis Plan  
 Protocol Number: 2125-MEL-301

Figure Title	Timing of Analysis
14.1.7.1 Kaplan-Meier Plot of Independent Reviewer-Assessed PFS by RECIST v1.1, Intent to Treat Analysis Set	Final
14.1.7.2 Kaplan-Meier Plot of Investigator-Assessed PFS by RECIST v1.1, Intent to Treat Analysis Set	Final
14.2.1 Boxplot of Hematology by Visit, Safety Set	IDMC, ORR, Final
14.2.2 Boxplot of Chemistry by Visit, Safety Set	IDMC, ORR, Final
14.2.3 Liver Function Tests Maximum Values to ULN on Study vs Baseline to ULN, Safety Set	ORR, Final
14.2.4 Mean (+/-SE) Change from Baseline in EORTC QLQ-30 Assessment Scores and Sub-Scale by Visit, Intent to Treat Analysis Set	ORR, Final

Idera Pharmaceuticals, Inc.  
 Statistical Analysis Plan  
 Protocol Number: 2125-MEL-301

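### The waterfall plot of injected versus non-injected lesions (SAP 10.2.3, Figure 14.1.3) is limited to responders, so it selects subjects on the tumour shrinkage it displays

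*SAP*

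**What the plan says.** SAP 8.2.8.2 gives the purpose: "To explore the treatment effect of IMO-2125 between the measurable injected and non-injected lesions". SAP 10.2.3 confines the analysis to the combination arm. It calculates, at each visit, the percent reduction in injected lesions, the same in non-injected lesions, and the within-subject difference. New lesions are left out.

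For the figure, 10.2.3 narrows the population: "The maximum percent reduction in SLD/SSD by injection status will be presented graphically in a waterfall plot for the ORR responders", judged by independent review under RECIST v1.1. The figure list in SAP 16.2 repeats the limit for Figure 14.1.3: "by Injection Status for ORR Responders, Intent to Treat Analysis Set". The SAP modification history records it as a version 2.0 change, so it is deliberate.

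Protocol 20.2 defines PR on target lesions as "Greater than or equal to 30% decrease under baseline of the sum of diameters of all target measurable lesions". Targets are "All measurable lesions up to a maximum of 2 lesions per organ, 5 lesions in total". Protocol 9.3.3.2 directs injection to one chosen lesion, with a switch allowed if a full dose no longer fits. Protocol 11.1 allows injected lesions to be targets.

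Three other outputs on this question have no responder limit:
- Table 14.2.2, the paired differences (ITT);
- Listing 16.2.2.1.7, lesion sums by injection status (ITT);
- a spider plot by injection status, named in 10.2.3. It is missing from the 16.2 figure list, where the spider plots (14.1.2.3 and 14.1.2.6) are not split by injection status.

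**The concern.** The figure is meant to show how injected and non-injected lesions behave. It keeps only subjects whose combined target lesions shrank enough for a response. With one lesion injected and up to five targets, non-injected lesions will often make up much of that sum, so the plot conditions on the quantity it shows.

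Activity at distant sites is part of the drug's stated rationale (Protocol 4.3.1.1, 4.4.3 and 4.4.4). A reader who sees non-injected bars pointing down in nearly every subject may take that as evidence of a distant effect, although the selection rule would produce much of the pattern without one. Because the spider plot is not listed, Figure 14.1.3 is the only listed figure on the question. The SAP's other waterfall plots (Figures 14.1.2.2 and 14.1.2.5) use the ITT set without this limit.

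**Working it through.** **1. The plan's own figures, for scale.** The plan states no number for this plot. The nearest is the ORR power: 12% versus 24%, 227 per arm (454/2), one-sided alpha 0.02, stated power 90%.

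- z = [0.12 x sqrt(227) - 2.054 x sqrt(2 x 0.18 x 0.82)] / sqrt(0.12 x 0.88 + 0.24 x 0.76) = (1.808 - 1.116) / 0.537 = 1.29, so power is 0.901. The plan's figure reproduces.
- At a 24% response rate the figure would show about 0.24 x 227 = 54 Arm B subjects; at 12%, about 27. The rest of the 227 would be left out.

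**2. What PR requires of the non-injected targets.** Let w be the injected share of the baseline target sum and s the fractional shrinkage of the injected lesion. PR needs w x s + (1 - w) x n >= 0.30, so the non-injected targets must shrink by at least n = (0.30 - w x s) / (1 - w).

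| w | s = 30% | s = 50% | s = 100% |
|---|---|---|---|
| 0 (injected lesion not a target) | 30% | 30% | 30% |
| 0.2 | 30% | 25% | 12.5% |
| 1/3 | 30% | 20% | none (5% growth allowed) |
| 0.5 | 30% | 10% | none (40% growth allowed) |

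Example: w = 0.2 and s = 1 gives (0.30 - 0.20) / 0.80 = 12.5%. The requirement disappears only when the injected lesion is a large share of the sum and nearly vanishes.

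**3. Simulation with no distant effect.** The documents give no standard deviations, injected share or local effect, so all of these are assumptions. Each scenario has 400,000 subjects and changes floored at -100%. Response means w x (injected change) + (1 - w) x (non-injected change) <= -30%. Non-injected changes have mean 0. In all subjects the mean non-injected change is about 0%, and 50% show shrinkage.

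Moderate local effect (injected mean -30, both SDs 40 points, independent), responders only:
- w = 0.5: mean non-injected change -33%, 86% shrinking
- w = 0.33: -46%, 99%
- w = 0.2: -51%, 100%
- correlation 0.3 to 0.6, w = 0.5 or 0.33: means -36% to -45%

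Stronger local effect (injected mean -60, SD 30, independent), responders only:
- non-injected SD midway between 20 and 30: about -13% at w = 0.5 and -26% at w = 1/3
- non-injected SD 20 to 30: -9% to -17% at w = 0.5, and -21% to -31% at w = 1/3. The w = 0.5 cases imply a response rate near 50%, far above the planned 24%.

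The side-by-side contrast is distorted too. With the moderate local effect and independence, the true injected-minus-non-injected gap is about -29 points. Among responders it falls to about -4 at w = 0.33 and reverses to about +10 at w = 0.2. Correlation between the two changes weakens this.

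**4. A second model.** Lognormal subject and lesion effects, one injected and four non-injected lesions, calibrated to 12% response on ipilimumab alone. The injected share runs from 0.2 to 0.5, and the local effect is either none or an extra 50% shrinkage. There is no distant IMO-2125 effect.

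| Non-injected lesions | All subjects | Responders |
|---|---|---|
| Median change | -8% to +12% | -19% to -40% |
| Share with any shrinkage | 38% to 63% | 91% to 100% |
| Share with at least 30% shrinkage | 11% to 14% | 22% to 93% |

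Simulated ipilimumab-alone responders, with nothing injected, show medians of -28% to -40% in the same lesions.

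**5. Limits of the models.** Both use one change per subject, whereas the figure takes the maximum reduction over visits. In the first model the plotted lesions are exactly those that decide response; the figure can also include measured non-target lesions.

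**The case against.** - *The unrestricted analysis is already planned.* This stands. Table 14.2.2 and Listing 16.2.2.1.7 serve the purpose in 8.2.8.2 without selecting on response. A reader might infer that the whole injected-versus-non-injected analysis is responder-only; the SAP does not support that.
- *The restriction is open.* This stands. Both figure titles name responders and the modification history records the choice, so no extra label is needed.
- *A responder plot answers a narrower question: is a RECIST response carried by the injected lesion alone?* This stands in part. A reader might infer that shrinkage is forced and the figure uninformative. That goes too far: where the injected lesion dominates and nearly vanishes, response needs no distant shrinkage. In the half-burden case above, 14% of responders show none. An all-subject plot with responders marked still answers this question.
- *The size rests on assumptions.* This stands. The direction is the same in every scenario, but the amount is uncertain.
- *An all-subject figure would not isolate a distant IMO-2125 effect either.* This stands. Ipilimumab acts systemically and the analysis has no control arm.
- *Nothing formal depends on it.* This stands. The comparison is not a listed endpoint, it is called exploratory, and it carries no alpha.
- *The missing spider plot is clerical.* This stands. Section 10.2.3 commits to it, and the list only needs to match.

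**Conclusion.** The point holds for one descriptive figure and is minor. Figure 14.1.3 selects on the shrinkage it displays, so non-injected shrinkage in it is weak evidence of a distant effect. With no such effect, responders would typically show a mean non-injected change of about -13% to -50%, against about 0% in all subjects. These figures rest on assumed SDs, injected share and local effect; the less plausible corner in the working gives -9%. The algebra in step 2 needs no distributional assumption.

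The documents do not support reading this as a flaw in the SAP's whole lesion-level analysis, as a hidden selection, or as a threat to the primary tests, alpha or any endpoint.

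**What to change.** 1. Draw Figure 14.1.3 for all Arm B subjects with at least one measurable injected and one measurable non-injected lesion at baseline and a post-baseline measurement. Mark responders by colour. Amend 10.2.3 and the 16.2 title to match.
2. Add the spider plot by injection status promised in 10.2.3 to the 16.2 figure list.
3. State beside both figures that they do not isolate a distant IMO-2125 effect, because all Arm B subjects are also assigned systemic ipilimumab and the analysis has no ipilimumab-alone comparator. Refer the reader to Table 14.2.2.

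Cost: a change of figure population, one list entry and a footnote, with no new data. The plot will be more crowded (up to 227 subjects instead of about 54 at the planned 24% response rate) and will probably look less favourable.

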#### **10.2.4 Durable Response Rate**

The durable response rate will be derived separately for the assessments by blinded independent reviewer and the investigator. DRR will be derived using RECIST v1.1, defined as the rate of CR or PR lasting  $\geq 6$  months from the date of first instance of confirmed CR or PR response which begin during the first 12 months of treatment. The denominator will be the number of subjects included in the corresponding analysis set (e.g., ITT). The calculation for the number of days in 6 months is  $6 \times (365.25/12)$ ; the cutoff date for 6 months is therefore (scan date + 182.625).

Summaries will include DRR by RECIST v1.1 with corresponding 95%, two-sided CIs using the Wald's binomial method for each treatment arm.

Summaries of DRR are included within the following summary outputs:

- DRR based on Independent Reviewer-Assessed ORR by RECIST v1.1
- DRR based on Investigator-Assessed ORR by RECIST v1.1

Note: DRR analyses are included in the Independent Reviewer-Assessed Response and Investigator-Assessed Response by RECIST v1.1 tables.

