15.3. Missing Data

Missing data occurs when any requested data is not provided, leading to blank fields on the collection instrument. These data will be indicated by the use of a “blank” in subject listing displays. Answers such as “Not applicable” and “Not evaluable” are not missing.

All available OS, PFS, and duration of response data will be analyzed using suitable statistical methods; subjects with shorter treatment and follow-up due to the natural history of their disease, or medical necessities of the treatment of their disease will not be considered to have missing time-to-event data. For ORR and DRR, all subjects in the ITT population will be included in the denominator when calculating the percentages; that is, the imputed response will be negative. Missing QoL data from the EORTC QLQ-C30 will be imputed using the methods prescribed for EORTC QLQ instruments.

Subjects with the designation of treatment relationship for AEs and SAEs missing will have the worst case assumed to impute the relationship: if relationship to study treatment is missing it will be assumed to be “Yes”.

Partial dates will be imputed for AEs and concomitant medications. Imputed dates are will not be used for deriving the last contact date for OS. Imputed dates will be displayed in listings and identified as imputed. Full details of imputing missing data and rules for analysis of measures with missing data will be included in the Statistical Analysis Plan (SAP).

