## **10.1 ANALYSIS OF THE PRIMARY ENDPOINT FAMILY**

### **10.1.1 Independent Reviewer-Assessed ORR by RECIST v1.1**

The final and sole analysis of ORR assessed by blinded independent review using RECIST v1.1 will test the response proportions of the two treatment arms using a stratified Cochran-Mantel-Haenszel (CMH) test for two proportions by the randomized strata as defined in [Section 9.4](#). To allow for adequate time for response and confirmation, the analysis of ORR will take place no sooner than when all randomized subjects completed scheduled study treatment and completed at least 28 weeks on the study; prematurely discontinued study treatment and completed at least 28 weeks on the study; or withdrew, were lost to follow-up, or died before completing at least 28 weeks on the study.

The generic SAS procedure call is:

```
proc freq data=<dataset name>;
  tables strata*response*treatment / cmh ;
run;
```

ORR is defined as the percentage of subjects achieving a CR or PR out of the total number of subjects included in the analysis population. The CR or PR must occur prior to PD and the start of any subsequent anticancer therapy. Subjects with not evaluable, unknown, or missing best response will be handled as non-responders; i.e., they will be included in the denominator when calculating the ORR. The independent reviewer-assessed best overall response and ORR by RECIST v1.1 with 95%, two-sided, confidence intervals (CIs) using the Wald's binomial method will be provided for each treatment arm. The percentage difference of ORR between the two treatment arms with a 95%, two-sided CI, and the p-value from the stratified CMH test will be provided. In support of ORR analysis, the

Idera Pharmaceuticals, Inc.  
Statistical Analysis Plan  
Protocol Number: 2125-MEL-301

---

summary statistics for duration of active follow-up times for all subjects will be provided (see the summary under subject disposition).

The following summary and figures will be provided:

- Independent Reviewer-Assessed Response by RECIST v1.1
- Swimmer's Plot of Independent Reviewer-Assessed Response by RECIST v1.1 for ORR Responders
- Waterfall Plot of Maximum Percent Reduction from Baseline in Individual Sum of the Longest Diameters of Target Lesions, Assessed by Independent Reviewer
- Spider Plot of Individual Percent Change from Baseline in Sum of the Longest Diameters of Target Lesions Over Time, Assessed by Independent Reviewer

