## 16.2 LIST OF TABLES, LISTINGS, AND FIGURES

The IDMC TLFs will be generated based on the schedule as defined in the Charter. The analysis of ORR will take place after all the randomized subjects either completed scheduled study treatment and completed at least 28 weeks on the study, prematurely discontinued study treatment and completed at least 28 weeks on the study, or withdrew, were lost to follow-up, or died before completing at least 28 weeks on the study. The final study analysis will take place when 392 deaths or approximately 36 months after the last subjects is randomized, whichever occurs first. All tables, figures, and listings will be produced for the final study analysis.

Tables, figures, and listings that will be produced for the IDMC meetings are identified with IDMC, the additional TLFs requested by IDMC during the course of the study are confidential and will not be included in the list below; and the final analysis of objective response rate with ORR, and the final analysis of OS with Final. The page header will indicate the timing of the analysis.

Table Title	Timing of Analysis
14.1.1.1 Subject Disposition, All Subjects *	IDMC, ORR, Final
14.1.1.2 Subject Disposition, Full Analysis Set	ORR, Final
14.1.1.3 Subject Disposition, Per Protocol Analysis Set	ORR, Final
14.1.2 Duration of Active Follow-up Times, Intent to Treat Analysis Set	ORR, Final
14.1.3 Major Protocol Deviations by Category, Intent to Treat Analysis Set	ORR, Final
14.1.4.1 Demographic Characteristics, Intent to Treat Analysis Set *	IDMC, ORR, Final
14.1.4.2 Demographic Characteristics, Full Analysis Set	ORR, Final
14.1.4.3 Demographic Characteristics, Per Protocol Analysis Set	ORR, Final
14.1.5.1 Baseline Disease Characteristics, Intent to Treat Analysis Set	IDMC, ORR, Final
14.1.5.2 Baseline Disease Characteristics, Full Analysis Set	ORR, Final
14.1.5.3 Baseline Disease Characteristics, Per Protocol Analysis Set	ORR, Final
14.1.6.1 Prior Systemic Anticancer Treatment History in All Settings, Intent to Treat Analysis Set	IDMC, ORR, Final

Idera Pharmaceuticals, Inc.  
 Statistical Analysis Plan  
 Protocol Number: 2125-MEL-301

Table Title	Timing of Analysis
14.1.6.2 Prior Systemic Anticancer Treatment History in Unresectable/Metastatic Disease Setting Only, Intent to Treat Analysis Set	ORR, Final
14.1.7.1 Stratification Factor Levels as Randomized, Intent to Treat Analysis Set	ORR, Final

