14.1.7.2 Stratification Factor Levels from the Clinical Data, Intent to Treat Analysis Set	ORR, Final
14.1.8.1 Concomitant Medications, Safety Set	ORR, Final
14.1.8.2 Concomitant Medications for irAEs by Category, Safety Set	IDMC, ORR, Final
14.1.8.3 Cancer Treatments and Surgeries after Start of Study Treatment, Safety Set	ORR, Final
14.2.1.1.1 Summary of Independent Reviewer-Assessed Response by RECIST v1.1, Intent to Treat Analysis Set *	ORR, Final
14.2.1.1.2 Sensitivity Analysis: Summary of Objective Response Rate by RECIST v1.1, Full Analysis Set	ORR, Final
14.2.1.1.3 Sensitivity Analysis: Summary of Objective Response Rate by RECIST v1.1, Per Protocol Analysis Set	ORR, Final
14.2.1.1.4 Sensitivity Analysis: Un-Stratified and Best Case Scenario Analysis of Objective Response Rate by RECIST v1.1, Full Analysis Set	ORR, Final
14.2.1.2 Summary of Investigator-Assessed Response by RECIST v1.1, Intent to Treat Analysis Set *	ORR, Final
14.2.1.3.1 Concordance of Best Overall Response by Independent Reviewer and Investigator, Intent to Treat Analysis Set *	ORR, Final
14.2.1.3.2 Concordance of Objective Response Rate by Independent Reviewer and Investigator, Intent to Treat Analysis Set	ORR, Final
14.2.1.4.1 Subgroup Analysis: Summary of Objective Response Rate by RECIST v1.1 by Metastasis Stage, Intent to Treat Analysis Set	ORR, Final
14.2.1.4.2 Subgroup Analysis: Summary of Objective Response Rate by RECIST v1.1 by BRAF Mutation and Prior Targeted Therapy, Intent to Treat Analysis Set	ORR, Final

Idera Pharmaceuticals, Inc.  
 Statistical Analysis Plan  
 Protocol Number: 2125-MEL-301

Table Title	Timing of Analysis
14.2.1.4.3 Subgroup Analysis: Summary of Objective Response Rate by RECIST v1.1 by Duration of Prior Anti-PD-1 Therapy, Intent to Treat Analysis Set	ORR, Final
14.2.1.4.4 Subgroup Analysis: Summary of Objective Response Rate by Country, Intent to Treat Analysis Set	ORR, Final
14.2.1.4.5 Subgroup Analysis: Summary of Objective Response Rate by Baseline ECOG, Intent to Treat Analysis Set	ORR, Final
14.2.1.4.6 Subgroup Analysis: Summary of Objective Response Rate by Baseline LDH, Intent to Treat Analysis Set	ORR, Final
14.2.1.4.7 Subgroup Analysis: Summary of Objective Response Rate by RECIST v1.1 by Baseline Neutrophil/Lymphocyte Ratio, Intent to Treat Analysis Set	ORR, Final

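### Durable response rate is tabulated at the ORR cut before late-enrolled responders can reach 6 months, so that topline figure is biased low; the Final figure is not

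*SAP*

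**What the plan says.** **Definition.** SAP 10.2.4 counts a CR or PR lasting at least 6 "months from the date of first instance of confirmed CR or PR response which begin during the first 12 months of treatment". It sets 6 months at 182.625 days from the scan date and reports a simple proportion with a Wald interval. The denominator is the whole analysis set. Protocol 15.3 agrees: "For ORR and DRR, all subjects in the ITT population will be included in the denominator when calculating the percentages". Neither section says how to classify a response that is still ongoing at under 6 months.

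**Where and when it is reported.** SAP 10.2.4 notes: "DRR analyses are included in the Independent Reviewer-Assessed Response and Investigator-Assessed Response by RECIST v1.1 tables". In SAP 16.2 the independent-review table, "14.2.1.1.1 Summary of Independent Reviewer-Assessed Response by RECIST v1.1, Intent to Treat Analysis Set", and its investigator counterpart (14.2.1.2) are both timed for the ORR analysis and the Final analysis. Both carry the asterisk that the list explains as topline output.

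**ORR trigger.** SAP 10.1.1 allows the ORR analysis "no sooner than when all randomized subjects completed scheduled study treatment and completed at least 28 weeks on the study", with parallel categories for subjects who stopped treatment or left the study.

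**Final.** SAP 16.2 adds: "All tables, figures, and listings will be produced for the final study analysis". DRR is therefore produced twice.

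**Status.** Protocol 15.4.2 and SAP 7.2 make DRR descriptive, with no test.

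**The concern.** A binomial proportion treats every subject as fully observed. DRR can need up to about 18 months of follow-up (12 months for onset plus 6 for duration), but the ORR cut guarantees only 28 weeks for the last subjects. A late-enrolled responder whose response is intact at the cut stays in the denominator and cannot enter the numerator.

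The same output package handles that person differently elsewhere. Duration of response (DoR) is also produced at the ORR cut, and there SAP 10.2.6 censors ongoing responses. PFS and OS summary tables are held back to Final. DRR reaches the ORR cut only because its rows sit inside the response tables.

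At stake is a named secondary endpoint shown in topline tables with an interval that treats incomplete follow-up as failure, and with nothing in the table to say so.

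**Working it through.** **Inputs**
- Threshold 182.625 days, onset within 12 months: SAP 10.2.4.
- Scans at Week 12, every 8 weeks in year 1, then every 12 weeks: Protocol 11.1.
- Minimum 28 weeks on study for the last subjects: SAP 10.1.1.
- About 20 months of uniform accrual: SAP 4.5 and Protocol 15.1. This is a planning assumption for OS power. Actual accrual is not in the documents, so 12 and 30 months are also shown.
- Timing of first response: not in the documents; assumed, with a range.

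**Step 1: the plan's own figure.** 6 × 365.25/12 = 182.625 days, which reproduces exactly; 182.625/7 = 26.09 weeks.

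**Step 2: earliest durable response.** 12 + 26.09 = Week 38.1. A subject with 28 weeks of follow-up cannot qualify.

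**Step 3: share of responders without enough follow-up.** 20 months is 20 × 30.4375/7 = 86.96 weeks. Follow-up at the cut is then uniform from 28 to about 115 weeks (6.4 to 26.4 months). For onset at week w, the share is (w + 26.09 − 28)/86.96. The last column replaces w + 26.09 by the next scheduled scan.

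| Onset (week) | 6 months reached (week) | Share short | Next scan (week) | Share short if scan needed |
|---|---|---|---|---|
| 12 | 38.1 | 11.6% | 44 | 18.4% |
| 20 | 46.1 | 20.8% | 52 | 27.6% |
| 28 | 54.1 | 30.0% | 64 | 41.4% |
| 36 | 62.1 | 39.2% | 64 | 41.4% |
| 44 | 70.1 | 48.4% | 76 | 55.2% |
| 52 | 78.1 | 57.6% | 88 | 69.0% |

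For Week 12 onset, accrual of 12 months gives 10.09/52.18 = 19.3%, and 30 months gives 10.09/130.45 = 7.7%.

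**Step 4: relative shortfall in DRR.** If enrolment date is unrelated to onset and duration, the fraction of truly durable responses missed is the average of these shares over the onset mix.
- 80/15/5% at Weeks 12/20/28: 0.80 × 11.6 + 0.15 × 20.8 + 0.05 × 30.0 = 13.9%.
- 50/30/20%: 0.50 × 11.6 + 0.30 × 20.8 + 0.20 × 30.0 = 18.0%.
- 70/20/10%: 15.3%, or 22.5% if the scan is needed.
- 30/25/20/10/10/5% at Weeks 12 to 52: 26.3%, or 33.8% if the scan is needed.

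**Step 5: absolute scale (illustration).** Take the design ORRs of 24% and 12% and assume exponential DoR with a 12-month median. Mature DRR is 24% × 2^(−0.5) = 17.0% against 8.5%, a difference of 8.5 points. A 14% shortfall shows 14.6% against 7.3% (7.3 points), 18% shows 13.9% against 7.0% (about 7.0 points), and 34% shows 11.2% against 5.6% (5.6 points). The ratio stays at 2 if onset timing is the same in both arms.

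**Step 6: Final.** With medians of 11.4 and 16.85 months, exponential survival and no dropout, expected deaths are 381 at month 48 and 394 at month 52, so 392 falls at about month 51-52, roughly 31 months after the last subject. Even if both arms had the 11.4-month median, expected deaths at month 44 are 454 × (1 − 0.1345) = 393, 24 months after the last subject. The mean survival of 0.1345 is (e^(−0.0608×24) − e^(−0.0608×44))/(0.0608×20). Both exceed the 18 months that DRR can need, and also Week 88 (20.2 months), so the shortfall at Final is about zero.

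**The case against.** The strongest reply is that the plan already delivers a mature DRR at Final. DRR is untested, and the ORR-timed package shows its own immaturity: Kaplan-Meier DoR with the number censored (also starred as topline), swimmer plots of responders, and a summary of active follow-up in support of ORR. All of this stands. It limits the consequence but does not correct the DRR row, which carries no flag and no count.

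It is also fair to say that 28 weeks is the minimum for the last subjects and not everyone's follow-up. The working allows for this, and it is why the shortfall is moderate.

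Third, no sentence in the SAP says that ongoing short responses are failures. The negative imputation in Protocol 15.3 and SAP 8.1.1 concerns missing data, and a documented ongoing response is not missing. That is correct. The classification is the default result of a whole-set denominator and a 6-month criterion that has not yet been met, and no rule says otherwise.

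Finally, the size rests on assumed onset timing and on planned accrual, which is why ranges are given.

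**Conclusion.** The point holds for the ORR-timed output only. DRR there is biased low by about 14-18% in relative terms with 20-month uniform accrual and first responses by Week 28, and by about 15-34% across wider onset mixes and the scan requirement. Shorter accrual makes it worse and longer accrual makes it milder. It is a minor point: no alpha or hypothesis test depends on DRR.

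A reader might infer more than the documents support:
- That the endpoint itself is understated. It is not; the same tables are rerun at Final with the window complete.
- That more than half of subjects are affected. With 20-month accrual, 58% lack the full 18 months at the ORR cut, but that matters only for responses starting near month 12. For Week 12 onsets the share is 11.6%.
- That the treatment comparison is reversed or distorted in ratio. With similar onset timing in both arms the ratio is kept and only the absolute difference shrinks.
- That this would be the leading public or regulatory figure. The documents say only that the tables are topline.

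Protocol 15.4.2 describes DRR as estimated among subjects with at least a PR, which conflicts with the whole-set denominator in Protocol 15.3 and SAP 10.2.4. That is a separate matter to reconcile.

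**What to change.** In SAP 10.2.4 and 16.2, report the DRR rows at Final only and name that the definitive estimate. At the ORR cut, add to the DoR tables already planned the Kaplan-Meier probability, by arm, that a response lasts at least 6 months. Describe it as conditional on response: it supplements the ITT-based DRR and does not replace it.

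If DRR is kept at the ORR cut, state how responses ongoing at under 6 months are classified, label the row immature, and give the number of such responses by arm.

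The cost is small. The DRR rows must be dropped from, or footnoted in, the ORR-timed versions of tables 14.2.1.1.1 and 14.2.1.2, and one landmark row is added to each DoR table. Under the preferred option no ITT-based DRR is shown until Final. No new data are needed and no test changes.
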